9.1. Determination of Sample Size

The study will screen an estimated 1833 potential study participants to ensure a minimum of approximately 825 patients. Based on the assumption of an effect size of 0.33 and a dropout rate of approximately 15%, the minimum sample size of 825 provides more than 90% power that at least 1 dose of LY2951742 will separate from placebo at a two-sided significance level of 0.05 based on simulations using Dunnett (Dunnett 1955) test. The 825 patients will be randomized in a 2:1:1 ratio to placebo (target of 413 patients), 120 mg/month of LY2951742 (target of 206 patients), or 240 mg/month (target of 206 patients), with the opportunity to increase the final sample size at an interim analysis if indicated to maintain a well-powered study. To preserve blinding, details of the sample size and power calculations are omitted from this protocol and are provided to the ERB in a separate document.

Approximately 100 sites in 11 countries are planned for inclusion in Study CGAI, with an average of approximately 8 patients to be randomized at each investigative site. The final number of sites, countries, and patients per site may vary depending on sites' enrollment rates and whether sample size is increased to maintain power.

9.2. General Statistical Considerations

Statistical analysis of this study will be the responsibility of Lilly or its designee. Details of statistical analysis methods will be described in the statistical analysis plan (SAP) document.

Unless otherwise specified, analyses will be conducted on an intent-to-treat (ITT) population, which will include all patients who are randomized and receive at least one dose of investigational product. Patients in the ITT population will be analyzed according to the treatment group to which they are randomized. When change from baseline is assessed, the patient will be included in the analysis only if he/she has a baseline and a postbaseline measurement.

Randomization will be stratified based on the frequency of acute headache medication intake during the 30-day baseline as yes/no overuse of acute headache medications. In addition, concomitant prophylaxis use will also be stratified.

For some of the analyses of the open-label treatment phase (Study Period IV), the open-label treatment population will be used. Open-label treatment population will be defined as all patients who entered the open-label treatment phase as indicated by receiving study drug at Visit 7. Patients in the open-label treatment population will be analyzed according to the treatment to which they were randomized in the double-blind period (Study Period III), as appropriate.

The primary analyses will be performed using a restricted maximum likelihood-based mixed models repeated measures (MMRM) technique with prespecified model terms (Section 9.4.1).

Visitwise binary efficacy variables will be analyzed using a generalized linear mixed model (GLIMMIX) as pseudo-likelihood-based mixed effects repeated measures analysis.

In addition to the MMRM approach, analysis of covariance (ANCOVA) model or analysis of variance (ANOVA) with the last-observation-carried-forward (LOCF) will also be implemented. When an ANCOVA model is used to analyze a continuous variable, the model will contain the main effects of treatment and pooled country, baseline medication overuse (yes/no), concomitant prophylaxis use (yes/no), as well as the continuous fixed covariates of baseline. The ANOVA model will use the same terms except the continuous fixed covariates of baseline. Type III sum-of-squares for the least-squares means will be used for the statistical comparisons.

Continuous efficacy and health outcome endpoints will be analyzed using MMRM methods, as well as an ANCOVA model with LOCF imputation if deemed appropriate.

Categorical comparisons between treatment groups will be performed using Cochran-Mantel-Haenszel (CMH) controlling for pooled country and using Fisher's exact test, where appropriate.

Countries will be pooled as deemed necessary for statistical analysis purposes.

Treatment effects will be evaluated based on a 2-sided significance level of 0.05 for all the efficacy and safety analyses unless otherwise stated. The 95% confidence intervals for the difference in least-square means between treatment groups will be presented. Adjustments for multiple comparisons for the analyses corresponding to the primary and secondary objectives for potential label inclusion are described in the sections on the primary and secondary efficacy analyses below. There will be no adjustments for multiplicity for analyses of other data.

Any change to the data analysis methods described in the protocol will require an amendment ONLY if it changes a principal feature of the protocol. Any other change to the data analysis methods described in the protocol, and the justification for making the change, will be described in the clinical study report or SAP. Additional exploratory analyses of the data will be conducted as deemed appropriate.

9.3. Treatment Group Comparability

9.3.1. Patient Disposition

The number and percentage of ITT patients who complete the study or discontinue early will be tabulated for all treatment groups for double-blind treatment (Study Period III), open-label treatment (Study Period IV), and post-treatment follow-up (Study Period V) both overall and by visit. Patient allocation by investigator will be summarized for Study Period III for all ITT patients. Patient allocation by investigator will also be listed for all study periods.

9.3.2. Patient Characteristics

The following patient characteristics at baseline will be summarized by treatment group for all ITT patients.

- Demographic (age, gender, ethnic origin, height, weight, body mass index)
- Migraine headache, headache, variation of migraine/headache measures per 30day baseline period

- Alcohol, tobacco, caffeine and nicotine consumption
- Medical history and preexisting condition
- Medication overuse

Medical history and pre-existing conditions will be summarized by preferred term within system organ class (SOC).

9.3.3. Concomitant Therapy

The proportion of patients who received concomitant medication collected from eCRF as well as abortive medications collected through ePRO will be summarized for all ITT patients for the double-blind, open-label, and post-treatment phases separately.

9.3.4. Treatment Compliance

Not applicable.

9.3.5. Electronic Patient-reported Outcome Diary Compliance

ePRO dairy compliance at each 1-month period, including baseline, will be calculated. Diary compliance at each period is calculated as:

Actual number of diary days in the period Expected number of diary days in the period * 100

9.4. Primary and Secondary Analyses

9.4.1. Primary Analyses

The primary efficacy measure is the overall mean change from the baseline period in the number of monthly migraine headache days during the 3-month double-blind treatment phase, and the primary analysis will evaluate the efficacy of LY2951742 (120 or 240 mg/month) compared with placebo.

The primary analysis will be performed using a restricted maximum likelihood-based MMRM technique. The analysis will include the fixed categorical effects of treatment, pooled country, medication overuse (yes/no), concomitant prophylaxis use (yes/no), month, and treatment-bymonth interaction, as well as the continuous fixed covariates of baseline number of migraine headache days and baseline number of migraine headache days-by-month interaction.

An unstructured covariance structure will be used to model within-patient errors. The Kenward-Roger (Kenward and Roger 1997) approximation will be used to estimate denominator degrees of freedom. If the model does not converge with both the Hessian and the G matrix being positive definite under the default fitting algorithm used by PROC MIXED, the Fisher scoring algorithm will be implemented by specifying the SCORING option in SAS. If the model still

fails to converge, the model will be fit using covariance matrices of the following order specified by a decreasing number of covariance parameters until convergence is met:

- Heterogeneous Toeplitz
- Heterogeneous First-order autoregressive
- Toeplitz
- First-order autoregressive

When the unstructured covariance matrix is not utilized, the sandwich estimator (Diggle and Kenward 1994) will be used to estimate the standard errors of the fixed effects parameters. The sandwich estimator is implemented by specifying the EMPIRICAL option in SAS[®]. When the sandwich estimator is utilized, the Kenward-Roger approximation for denominator degrees of freedom cannot be used. Instead, the denominator degrees of freedom will be partitioned into between-subject and within-subject portions by the DDFM=BETWITHIN option in SAS[®]. SAS[®] PROC MIXED will be used to perform the analysis.

If the sample size is increased as a result of the interim analysis, the Cui, Hung, and Wang (CHW) procedure (Cui et al. 1999) will be applied to the primary endpoint to control the type I error at a one sided α =0.025 significance level. The CHW method ensures strong control of type 1 error when the sample size is increased in a data dependent manner.

If the sample size is increased as a result of the interim analysis, an unadjusted point estimate for the primary efficacy analysis will be calculated and reported. A median unbiased point estimate and a stage-wise adjusted confidence interval for the primary efficacy analysis will be calculated and reported based on the approach described by Brannath and colleagues (Brannath et al. 2009) to assess sensitivity of the point estimate.

9.4.2. Key Secondary Analyses

The key secondary objectives (see Table CGAI.1) will be tested using an appropriate multiple testing approach providing strong control of the familywise error rate (for the primary and key secondary tests) at a one-sided 0.025 alpha level (or, equivalently, two-sided 0.05 alpha level).

There will be no adjustments for multiplicity for analyses of other endpoints. If the multiple testing approach for key secondary measures only needs to be changed, the updated approach will be provided in the SAP, and it should not lead to modification of this protocol.

The key secondary measures will be analyzed for the double-blind treatment (Study Period III).

For the continuous key secondary measures, the change from baseline will be analyzed from repeated measures analyses as described in Section 9.4.1. For the categorical key secondary efficacy measure of 50%, 75%, and 100% response, the percentage of patients meeting response criteria during the 3-month double-blind treatment phase will be estimated for each treatment from a categorical, pseudo-likelihood-based repeated measures analysis of longitudinal binary

outcomes indicating whether patients meet response criteria. This analysis will be implemented using the GLIMMIX procedure in SAS.

If the sample size is increased, the CHW test statistic will be calculated for the primary and all the key secondary outcomes before applying the multiple testing procedure.

9.4.3. Other Secondary and Tertiary Efficacy Analyses

The other secondary and exploratory efficacy analyses will be conducted for the double-blind treatment, open-label treatment, and post-treatment phases.

For the continuous secondary and exploratory efficacy measures, the change from baseline to each 1-month period postbaseline measure will be analyzed from repeated measures analyses as described in Section 9.4.1.

In addition to the repeated measures analyses, the mean change from baseline to LOCF endpoint for each treatment will be estimated for the continuous efficacy measures using ANCOVA models as described in Section 9.2. Categorical analyses will use the same model as described in Section 9.4.2 (additional details are described in the SAP).

9.5. Safety Analyses

The safety analyses will be conducted for the double-blind treatment, open-label treatment, and post-treatment follow-up phases.

The safety and tolerability of treatment will be assessed by summarizing the following:

- adverse events
 - o treatment-emergent adverse events (TEAEs)
 - by preferred term
 - by SOC
 - by maximum severity
 - by outcome
 - considered to be related to investigational product by investigator
 - serious adverse event
 - o adverse event leading to discontinuation
- Suicidal ideation and behaviors assessed by solicited questioning using the C-SSRS
- Vital signs and weight
- electrocardiograms
- Laboratory measurements
- Anti-LY2951742 antibody

9.5.1. Categorical Safety Variables

Unless specified otherwise, the categorical safety analyses will include both scheduled and unscheduled visits.

Comparisons between treatment groups for all categorical safety measures will be made using the Fisher's exact test for Study Period III (double-blind treatment) with the ITT population.

9.5.2. Adverse Events

Treatment-emergent adverse events are defined as the reported AEs that first occurred or worsened during the postbaseline phase compared with baseline phase. For each TEAE, the severity level of the event (mild, moderate, or severe) will be determined by patient or physician opinion. The Medical Dictionary for Regulatory Activities (MedDRA) Lowest Level Term will be used in the treatment-emergent computation. For each Lowest Level Term, the maximum severity at baseline will be used as the baseline severity. If the maximum severity during postbaseline is greater than the maximum baseline severity, the event is considered to be treatment-emergent for the specific postbaseline period. For each patient and TEAE, the maximum severity for the MedDRA level being displayed (Preferred Term, High Level Term, or SOC) is the maximum postbaseline severity observed from all associated Lowest Level Terms mapping to that MedDRA level.

For events that are gender-specific, the denominator and computation of the percentage will include only patients from the given gender.

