Appendix 1. Abbreviations and Definitions

Term	Definition
AE	adverse event: Any untoward medical occurrence in a patient or clinical investigation subject administered a pharmaceutical product that does not necessarily have a causal relationship with this treatment. An adverse event can therefore be any unfavorable and unintended sign (including an abnormal laboratory finding), symptom, or disease temporally associated with the use of a medicinal (investigational) product, whether or not related to the medicinal (investigational) product.
complaint	A complaint is any written, electronic, or oral communication that alleges deficiencies related to the identity, quality, purity, durability, reliability, safety or effectiveness, or performance of a drug or drug delivery system.
enroll	The act of assigning a patient to a treatment. Patients who are enrolled in the trial are those who have been assigned to a treatment.
enter	Patients entered into a trial are those who sign the informed consent form directly or through their legally acceptable representatives.
ePRO	electronic patient-reported outcomes
interim analysis	An interim analysis is an analysis of clinical study data, separated into treatment groups, that is conducted before the final reporting database is created/locked.
investigational product	A pharmaceutical form of an active ingredient or placebo being tested or used as a reference in a clinical trial, including products already on the market when used or assembled (formulated or packaged) in a way different from the authorized form, or marketed products used for an unauthorized indication, or marketed products used to gain further information about the authorized form.
ІТТ	intent to treat: The principle that asserts that the effect of a treatment policy can be best assessed by evaluating on the basis of the intention to treat a patient (that is, the planned treatment regimen) rather than the actual treatment given. It has the consequence that patients allocated to a treatment group should be followed up, assessed, and analyzed as members of that group irrespective of their compliance to the planned course of treatment.
IWRS	interactive web-response system
SAE	serious adverse event
TEAE	treatment-emergent adverse event: Any untoward medical occurrence that either occurs or worsens at any time after treatment baseline and that does not necessarily have to have a causal relationship with this treatment.

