5.5.1.5. Baseline and Postbaseline Definition

Table CGAI.5.4 describes the rules for determining the patient population and baseline and postbaseline observations for each study phase and type of analysis. When "last of Visit x-x" is used in the table, the last nonmissing observation obtained in the visit interval will be used.

Table CGAI.5.4. Patient Population with Baseline and Postbaseline Definitions by Study Period and Type of Analysis

Study Period / Analysis	Patient Population	Baseline Observation	Postbaseline Observation(s)
Study Period III			
Efficacy analyses (Repeated Measures) or average of observed monthly values	ITT Population with a baseline and at least 1 postbaseline observation	Visit 3	All scheduled visits 3 < Visits ≤7
Efficacy analyses at LOCF endpoint		Visit 3	Last of Visit 3.01-7
Quality of Life analyses (Repeated Measures)		Visit 3	All scheduled visits 3 < Visits ≤7
Quality of Life analyses at LOCF endpoint or for average of observed monthly values		Visit 3	Last of Visit 3.01-7
TEAEs	Safety Population	All Visits 1–3	All Visits 3.01–7
Serious Adverse Events, Discontinuations due to Adverse Events	Safety Population	NA	All Visits 3.01–7
C-SSRS categorical analyses	Patients with a baseline and at least 1 postbaseline C-SSRS assessment	Recent History: Visits 1–3 excluding lifetime ^a All Prior History: Visits 1–3 including lifetime ^a	All Visits 3.01–7
Treatment-emergent abnormal laboratory values	Safety Population with normal laboratory values at all nonmissing baseline visits (with respect to direction being analyzed) and who have at least 1 postbaseline observation	Low: Minimum from Visits 1–3 High: Maximum from Visits 1–3 Abnormal: All Visits 1–3	Low: Minimum from Visits 3.01–7 High: Maximum from Visits 3.01–7 Abnormal: All Visits 1–3
Treatment-emergent immunogenicity	Safety Population	Visit 3	All Visits 3.01–7
Treatment-emergent changes in temperature and weight	Safety Population with a baseline and at least 1 postbaseline observation	Low: Minimum from Visits 1–3 High: Maximum from Visits 1–3	Low: Minimum from Visits 3.01–7 High: Maximum from Visits 3.01–7
Treatment-emergent changes in blood pressures, pulse, and ECGs	Safety Population with a baseline and at least 1 postbaseline observation	Low: Last non-missing from Visits 1–3 High: Last non-missing from Visits 1–3	Low: Minimum from Visits 3.01–7 High: Maximum from Visits 3.01–7

Patient Population with Baseline and Postbaseline Definitions by Study Period and Type of Analysis

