Study Period / Analysis	Patient Population	Baseline Observation	Postbaseline Observation(s)
Study Period III	•	.	
Continuous safety analyses (Repeated Measures)	Safety Population with a baseline and at least 1 postbaseline observation	Last of Visits 1–3	All scheduled visits 3 < Visits ≤7
Continuous safety analyses – change from baseline to LOCF endpoint (ANCOVA)	Safety Population with a baseline and at least 1 postbaseline observation	Last of Visits 1–3	Last of Visits 3.01–7
Study Period IV			
TEAEs	Open Label treatment Population	All Visits 1-7	All Visits 7.01–16
Serious Adverse Events, Discontinuations due to Adverse Events	Open Label treatment Population	NA	All Visits 7.01–16
Treatment-emergent abnormal laboratory values	Open Label treatment Population and Patients with normal laboratory values at all nonmissing baseline visits (with respect to direction being analyzed) and who have at least 1 postbaseline observation	Low: Minimum from Visits 1–7 High: Maximum from Visits 1–7 Abnormal: All Visits 1–7	Low: Minimum from Visits 7.01-16 High: Maximum from Visits 7.01-16 Abnormal: All Visits 7.01-16
C-SSRS categorical analyses	Open Label treatment Population and Patients with a baseline and at least 1 postbaseline C-SSRS assessment	Recent History: All Visits 1–7 excluding lifetime ^a All Prior History: Visits 1 – 7 including lifetime ^a	All Visits 7.01–16
Treatment-emergent immunogenicity	Open Label treatment Population	Visit 3	All Visits 7.01–16
Treatment-emergent changes in temperature and weight	Open Label treatment Population and Patients with a baseline and at least 1 postbaseline observation	Low: Minimum from Visits 1–7 High: Maximum from Visits 1–7	Low: Minimum from Visits 7.01–16 High: Maximum from Visits 7.01–16
Treatment-emergent changes in blood pressures, pulse, and ECGs	Open Label treatment Population and Patients with a baseline and at least 1 postbaseline observation	Low: last non-missing from Visits 1–7 High: last non-missing value from Visits 1–7	Low: Minimum from Visits 7.01–16 High: Maximum from Visits 7.01–16

Patient Population with Baseline and Post-baseline Definitions by Study Period and Type of Analysis

			Postbaseline
Study Period / Analysis	Patient Population	Baseline Observation	Observation(s)
Study Period V			
TEAEs	Post-treatment Population	All Visits 1- 16	All Visits 16.01–18
Serious Adverse Events, Discontinuations due to Adverse Events	Post-treatment Population	NA	All Visits 16.01–18

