5.5.12.1.1. Adverse Events

Treatment-emergent AEs are defined as the reported AEs that first occurred or worsened during the postbaseline phase compared with baseline phase. For each TEAE, the severity level of the event (mild, moderate, or severe) will be determined by patient or physician opinion. The MedDRA Lowest Level Term (LLT) will be used in the treatment-emergent computation. For each LLT, the maximum severity at baseline will be used as the baseline severity. If the maximum severity during postbaseline is greater than the maximum baseline severity, the event is considered to be treatment-emergent for the specific postbaseline period. For each patient and TEAE, the maximum severity for the MedDRA level being displayed (PT, High Level Term, or SOC) is the maximum postbaseline severity observed from all associated LLTs mapping to that MedDRA level. For events that are gender-specific, the denominator and computation of the percentage will include only patients from the specific gender.

5.5.12.1.1.1. Potential Hypersensitivity Events

Potential hypersensitivity events (immediate and non-immediate) will be identified from a review of preferred terms generated from the following queries:

- Anaphylactic reaction (SMQ 20000021)
- Broad and narrow terms in the Angioedema (SMQ 20000024)
- Broad and narrow terms in the Hypersensitivity (SMQ 20000214)

A listing of patients having an event identified from these analyses will be medically reviewed to determine if the terms identified represent actual hypersensitivity events. Listings should include information on timing of event relative to latest dose of study drug administration, the event term from this query, other AEs for the patient and timing, any abnormal laboratory findings, medical history and anti-drug antibody test results including titer. Only those that are judged medically to be hypersensitivity events will be included in the final tables.

The number and percentage of patients with TEAEs, SAEs, and AEs resulting in study drug discontinuation will be summarized by treatment groups using MedDRA PT nested within the SMQ. Events will be ordered by decreasing frequency within the SMQ.

The number and percentage of patients with treatment-emergent hypersensitivity events by maximum severity will be summarized by treatment groups using MedDRA PT.

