5.8.1.2. Reports to be Generated at Interim Analysis #2

At the time of interim analysis #2, all randomized patients will have had the chance to complete 3 months of treatment. The following analyses including tables, figures, and listings will be conducted for all randomized patients who have had a chance to complete 3 months of double-blind treatment phase (SP III):

- Patient disposition as specified in Section 5.5.2, for SP III and SP IV separately.
- Patient characteristics as specified in Section 5.5.4.
- Exposure to IMP as specified in Section 5.5.5, for SP III and SP IV separately.
- ePRO diary compliance as specified in Section 5.5.7, for SP III and SP IV separately.
- Previous migraine prevention therapy as specified in Section 5.5.8.
- Concomitant therapy as specified in Section 5.5.9, for SP III and SP IV separately.
- Efficacy analyses for the number of monthly migraine headache days, 50% response rate in the number of monthly migraine headache days, MSQ Role Function-Restrictive domain score, and PGI-S for SP III, and up to Month 9 in SPIV, as well as the proportion of patients who continue to demonstrate 50% response for at least 3 (not necessarily consecutive) of the first 6 months in the open-label treatment period.
- Safety analyses for TEAEs, and treatment-emergent changes in laboratory measures, vital signs, and ECG parameters for SP III and SP IV separately.
- ADA-related analyses for all data available, including SP III, SP IV, and SP V.
- All other efficacy, quality-of-life, and safety analyses as specified in Section 5.5.10, Section 5.5.11 and Section 5.5.12 for SP III only.

Analyses conducted at interim analysis #2 will be considered as the final analyses for double-blind treatment phase and will be used in the final CSR.

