5.9. Clinical Trial Registry Analyses

Additional analyses will be performed for the purpose of fulfilling the Clinical Trial Registry (CTR) requirements. These analyses will be the responsibility of the Sponsor.

Analyses provided for the CTR requirements include the following:

A summary of AEs will be provided as a dataset which will be converted to an XML file. Both SAEs and 'Other' AEs are summarized: by treatment group, by MedDRA PT.

- An AE is considered 'Serious' whether or not it is a TEAE.
- An AE is considered in the 'Other' category if it is both a TEAE and is not serious. For each SAE and 'Other' AE, for each term and treatment group, the following are provided:
 - o the number of participants at risk of an event
 - o the number of participants who experienced each event term
 - o the number of events experienced.
- Consistent with www.ClinicalTrials.gov requirements, 'Other' AEs that occur in fewer than 5% of patients in every treatment group may not be included if a 5% threshold is chosen.
- AE reporting is consistent with other document disclosures for example, the CSR, manuscripts, and so forth.

6. References

[ICHD-3] Headache Classification Committee of the International Headache Society (IHS). The International Classification of Headache Disorders, 3rd edition (beta version). *Cephalalgia*. 2013;33(9):629-808.

Permutt T. Sensitivity analysis for missing data in regulatory submissions. *Stat Med.* 2015;35:2876-2879.

7. Appendix: Description of Important Protocol Deviations

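### The open-label TEAE table uses a baseline that includes the double-blind period, so it omits recurrences at the same or lower severity and mixes on-drug and pre-drug baselines in one rate

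*Protocol*

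**What the plan says.** Protocol 9.5.2 describes treatment-emergent adverse events (TEAEs) as "reported AEs that first occurred or worsened during the postbaseline phase compared with baseline phase" and then gives the operating rule, applied by MedDRA Lowest Level Term (LLT): "If the maximum severity during postbaseline is greater than the maximum baseline severity, the event is considered to be treatment-emergent". It does not say which visits form the baseline for open-label treatment. SAP 5.5.12.1.1 repeats the rule and applies it period by period: "the event is considered to be treatment-emergent for the specific postbaseline period".

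The visit windows are in SAP 5.5.1.5, Table CGAI.5.4:

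- **SP III (double-blind):** baseline Visits 1 to 3; postbaseline "All Visits 3.01–7".
- **SP IV (open-label):** baseline Visits 1 to 7; postbaseline "All Visits 7.01–16".
- **Serious adverse events and discontinuations due to adverse events:** baseline not applicable in either period.
- **Treatment-emergent immunogenicity in SP IV:** baseline Visit 3.

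SAP 5.5.1.4 analyzes the open-label population as one group. SAP 5.8.1.2 schedules the SP IV output for interim analysis #2: "Safety analyses for TEAEs, and treatment-emergent changes in laboratory measures, vital signs, and ECG parameters for SP III and SP IV separately". SAP 5.5.12 and 5.5.12.1 also plan categorical safety analyses for SP III/IV combined, but Table CGAI.5.4 has no TEAE row for that combination.

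Appendix 1 of the protocol words the definition differently: "Any untoward medical occurrence that either occurs or worsens at any time after treatment baseline".

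**The concern.** A reader of an open-label TEAE table expects it to show how many patients had each event during open-label drug. Here it shows how many had an event that was new or worse than anything recorded since screening, including during the double-blind doses.

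For the half of patients randomized to LY2951742 (2:1:1 allocation, SAP 5.3), the reference period contains three monthly drug doses. For the other half it contains only placebo. The single-group rate therefore measures neither incidence on open-label drug nor first onset on drug.

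The tables most exposed are those built on TEAEs for events that can recur with dosing or over time: injection-site events, hypersensitivity and upper respiratory tract infections (SAP 5.5.12.1.1.1 to 5.5.12.1.1.3). A patient who reacted in SP III and reacts again no worse in SP IV stays in the SP IV denominator and leaves the numerator.

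There is a second mismatch. The SAP plans to relate hypersensitivity and injection-site TEAEs to treatment-emergent antidrug antibodies. If that is done for SP IV, antibodies are judged from Visit 3 and adverse events from Visits 1 to 7.

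**Working it through.** The plan states no figure on this point, so there is none to reproduce. The check has two parts.

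**1. What the rule does.** For one LLT, let *b*, *d* and *o* be the maximum severity (0 none, 1 mild, 2 moderate, 3 severe) in Visits 1 to 3, SP III and SP IV. The SP III rule is *d > b*. The planned SP IV rule is *o > max(b, d)*. A pre-drug comparison would be *o > b*.

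| Visits 1–3 / SP III / SP IV | SP III TEAE | SP IV TEAE as planned | SP IV against Visits 1–3 |
|---|---|---|---|
| none / mild / mild | yes | no | yes |
| none / moderate / mild | yes | no | yes |
| none / mild / moderate | yes | yes | yes |
| none / none / mild | no | yes | yes |

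There are 4 × 4 × 3 = 48 patterns with an event in SP IV. The planned rule drops 10 that the pre-drug comparison counts: 6 with *b* = 0, 3 with *b* = 1 and 1 with *b* = 2. With *b* = 0 there are 12 patterns; the planned rule drops 6 and the pre-drug comparison none. These are logical patterns, not patient frequencies.

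**2. How large it could be.** All rates below are assumptions; none is in the documents.

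*Population view.* Let *p* be SP III incidence, *r* the share of those patients who recur in SP IV at the same or lower severity, and *n* new onset in SP IV among the rest. Worse recurrences are left out.

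- Shown in the SP IV table: (1 − *p*)*n*. Omitted: *pr*. Omitted share: *pr* / [*pr* + (1 − *p*)*n*].
- *p* = 10%, *r* = 50%, *n* = 10%: shown 0.90 × 0.10 = 9.0%; omitted 0.10 × 0.50 = 5.0%; with the event 14.0%; omitted share 5.0/14.0 = 36%.
- Over *p* 5–20%, *r* 25–75%, *n* 5–10%: lowest 0.0125/(0.0125 + 0.095) = 12%; highest 0.15/(0.15 + 0.04) = 79%.

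*Per-dose view.* Take former-LY2951742 patients prone to an event with probability *q* at each dose. There are 3 double-blind and 9 open-label dosing visits (Protocol 6.1).

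- Constant severity: the masked share of those with an SP IV event is 1 − (1 − *q*)³ = 27%, 66% and 88% for *q* = 0.1, 0.3 and 0.5.
- If placebo injections cause no such events and arms enter SP IV in proportion, the pooled share is half of that: 14%, 33% and 44%.
- Varying severity, *q* = 0.5, with an assumed 70/25/5% mild/moderate/severe split, independent across doses. The SP IV maximum is mild, moderate or severe with probability 0.230, 0.565 and 0.204. The SP III maximum is at least that severe with probability 0.875, 0.386 and 0.073. Masked share: (0.230 × 0.875 + 0.565 × 0.386 + 0.204 × 0.073)/0.998 = 43%, against 88% with constant severity.

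**The case against.** The strongest reply is that this is a deliberate convention. In SP IV the laboratory, C-SSRS, temperature and weight categories also use Visits 1 to 7, and the SP V TEAE baseline is Visits 1 to 16. The resulting question, what is new or worse since entering the period, is legitimate. SP IV is summarized descriptively, so no test is biased. The recurring event is not lost from the safety record either: if it exceeded its Visits 1 to 3 severity it is an SP III TEAE, and an SP III/IV analysis with a pre-treatment baseline would count the patient once. All of this stands. What it does not supply is the number of patients with the event on open-label drug. The SP III/IV analysis would not isolate SP IV and has no TEAE baseline defined.

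SAP 5.5.12.1 refers to treatment groups in SP IV, so a display by prior arm may be intended. That would remove the mixing but not the omission.

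Four stronger readings are tempting and are not supported:

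- **That the rule contradicts Appendix 1.** A recurrence does occur after baseline, but Appendix 1 does not tie its treatment baseline to a study period. Read as the pre-randomization baseline, the event is already a TEAE in SP III. The wordings differ and need reconciling; a contradiction is not shown.
- **That 27% to 88% is the bias in the reported rate.** Those figures hold only for prone former-LY2951742 patients with constant severity.
- **That this rule is what makes SP IV rates incomparable with SP III.** SP IV is also open-label, nine months instead of three, and limited to patients who opt in.
- **That registry counts are distorted.** SAP 5.9 says "An AE is considered in the 'Other' category if it is both a TEAE and is not serious", but names no study period.

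**Conclusion.** The point holds as a limitation of the SP IV TEAE tables, and its source is the SP IV row of Table CGAI.5.4 read with the severity rule. The omission requires the same LLT and equal or lower severity; a different term or a worse severity is still counted. For former-placebo patients, an event on placebo that recurs no worse on first LY2951742 exposure is omitted too.

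The direction is certain: the SP IV rate cannot exceed, and will usually fall below, the proportion of patients with the event in that period. The size cannot be derived from the documents and runs from small to large with the assumed incidence, recurrence and severity pattern. No primary or between-group conclusion depends on it. It is an inexpensive improvement to the reporting of open-label safety, not a flaw in the trial's main inference.

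**What to change.** 1. Keep the present SP IV TEAE table, labelled as events new or worsened since SP III.
2. Add to Table CGAI.5.4 and to the planned outputs an SP IV summary of events that start or worsen after the Visit 7 injection, judged against the Visits 1 to 3 baseline for all patients and shown by prior randomized arm (placebo versus LY2951742). One baseline for everyone avoids mixing definitions, and the split keeps first exposure apart from continued exposure. Apply it to the injection-site, hypersensitivity and upper respiratory tract infection tables as well.
3. Add the missing SP III/IV TEAE row to Table CGAI.5.4 with a Visits 1 to 3 baseline.
4. Reconcile the wording of Appendix 1 with that of Protocol 9.5.2, and state which baseline applies in each period.

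The cost is two table rows, one more output and a wording change, with no new data. SP IV rates will look higher, and some events already reported in SP III will appear again; a footnote should say so.
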